## **7. Possible Discomforts and Risks:**

Study risks are minimal. The participants may become tired during the telephone intervention sessions. Breaks will be provided if needed. Also, some caregivers may feel uncomfortable or become stressed while discussing stroke-related issues that are affecting them. The interventionist(s) conducting the telephone interviews will receive extensive training and will have experience in assessing and caring for adults who have stress.

To further protect study participants from any risks, our intervention will be conducted by trained interventionist(s) with experience in conducting mental health assessments and counseling. We will hire an interventionist knowledgeable about caring for individuals and family members who are in stressful situations, such as involved in caregiving. Training of the interventionist(s) will include independent readings, didactic instruction, and role-playing. Throughout the project, the investigators will observe/listen to the interventionist(s) conducting the interventions and evaluate his or her fidelity to the protocol, decision-making skills, and how they handle the caregivers' problems and stress. If needed, select intervention sessions will be audio-recorded to facilitate fidelity checks if the participant agrees. Feedback and additional training, if needed, will be provided. The interventionists will make every effort to minimize the potential risks by maintaining a professional, pleasant manner and allowing caregivers to ask questions and discuss feelings. In the intervention arm, the interventionist(s) will assist the caregivers in solving their problems using the problem-solving approach. The interventionist(s) will not provide advice, but rather will advise caregivers to access information on the Caregiver Family Alliance website ([www.caregiver.org](http://www.caregiver.org)) for managing problems. In the event that the interventionist(s) assess that caregivers in any arm of the study are experiencing unmanageable, but not severe stress or depression, they will advise the caregivers to call their assigned VA social workers and primary care clinicians (MD, ARNP, PA). The interventionist(s) will also give the caregivers the phone number of the VA Caregiver Support Line. If the interventionist(s) assess that the caregivers are in severe stress, depression or crisis, or have serious changes in their health, the interventionist(s) will call either one of the study physician Co-investigators or the caregivers' VA primary care social workers and VA primary care healthcare providers (MD, ARNP, PA) immediately or 911 depending on the circumstances. If any abuse or neglect is suspected, study personnel will follow established procedures by oversight agencies including VHA as directed in the VA Handbook 1050.01 to contact the Office of Inspector General, Office of Investigation, as well as the IRB and the state of Abuse Hotline. We will train all study personnel to protect against all foreseeable risks. Team members also will be trained in monitoring and reporting adverse events.

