Recruitment calls will be made to potential participants identified from either of the three sites through the procedures described above by trained, Spanish speaking study staff in either Gainesville or PR. In addition to explaining study purpose and procedures, during the recruitment phone calls we will screen potential participants for study eligibility. Since all study procedures (except clinicians who will ask in person to potential participants if they would like to receive a call to obtain more information about our study) will be conducted over the telephone, we will request a Waiver Documentation of Informed Consent for this study. However, we will utilize an Informed Consent written statement to inform interested and eligible participants about the purpose of the study, study procedures including that some sessions may be recorded, risks, volunteer nature of their participation, potential benefits, who to contact in case of questions or concerns, etc. The written statement will also be used to inform and obtain oral permission to record the interventions. Since we will be requesting a Waiver Documentation of Informed Consent, we will also request a Waiver of master List of Consent and Re-consent. We will track the reasons for caregivers who decline to participate; no patient identifiable data will be collected for this purpose. We will recruit participants for 36 months and anticipate enrolling 8 caregivers per month. Even though we have strict eligibility criteria (see above), we expect that at least 10% of the potential caregivers will be willing to participate and meet our eligibility criteria. To collect Veteran healthcare utilization data, we will request a full waiver of consent to conduct the chart reviews.

**Randomization:** Following baseline assessments, participants will be randomly assigned to one of the two arms. The randomization will be blocked to ensure balanced group membership across time. The block size will be determined by the statistician and will not be shared with the rest of the team. The statistician will develop the randomization scheme and share it with a research staff member. The research staff member will prepare opaque randomization envelopes and provide them to the project coordinator (PC). The interventionist will call the PC when a caregiver is enrolled to obtain the caregiver's group assignment.

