**Data collection procedures:** Study personnel will follow a detailed, procedure manual, translated and adapted into Spanish from our previous pilot project, to collect the data. A data collector who is fluent in Spanish and has strong communication skills either in Gainesville or PR will be trained to conduct the assessments. Following enrollment and after going over the written statement script with eligible and interested study participants the data collector will contact caregivers at an agreed upon time to obtain demographic data and administer baseline survey questionnaires (see measures). To facilitate the collection of the baseline assessment, we will mail the demographic data form and questionnaires in advance for caregivers to read while the data collector asks questions and documents the caregivers' responses. We will also review the Veterans CPRS records and document the Veterans' age, gender, race/ethnicity, date/location/type of stroke, number of previous strokes, and resource use and any information related to the Veterans' care (treatments, medicines, patient and family education, case management, etc.). All caregivers who meet the study eligibility

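### The distress rule is meant for caregivers in any arm, but only interventionists can start it, and they have no planned contact with the standard-care arm

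*Combined protocol and SAP*

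**What the plan says.** Section 7 (Possible Discomforts and Risks) recognizes that caregivers may become stressed when talking about stroke-related problems, and it gives a graded response.

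- Lower tier: "In the event that the interventionist(s) assess that caregivers in any arm of the study are experiencing unmanageable, but not severe stress or depression", they advise the caregiver to call the assigned VA social worker and primary care clinician, and they give the number of the VA Caregiver Support Line.
- Severe tier: "If the interventionist(s) assess that the caregivers are in severe stress, depression or crisis", or that there is a serious change in health, they contact a study physician co-investigator or the VA social worker and primary care providers immediately, or 911, as circumstances require.

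The same section handles suspected abuse differently: "If any abuse or neglect is suspected, study personnel will follow established procedures by oversight agencies". It closes with general training for all personnel: "Team members also will be trained in monitoring and reporting adverse events".

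Section 6 says who speaks to caregivers. On recruitment, "Recruitment calls will be made to potential participants identified from either of the three sites" by Spanish-speaking study staff, and "during the recruitment phone calls we will screen potential participants for study eligibility". At baseline, "the data collector will contact caregivers at an agreed upon time to obtain demographic data and administer baseline survey questionnaires". The Data collection procedures give both post-tests to a data collector blinded to group, using the baseline instruments again. The Intervention paragraph gives the eight weekly sessions to an interventionist and limits them to the intervention group. The Aim 5 section has the data collector interview 8-12 intervention caregivers by telephone.

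**The concern.** The authors wrote a safety rule for every arm and then gave it to a role whose planned work lies in one arm only. This is more than a missing detail: followed as written, the rule has no planned occasion on which it could operate for a standard-care caregiver.

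What is at stake is participant safety. Eligibility requires at least moderate stress, the CES-D is asked at every assessment, and the Standard Care Group paragraph says these caregivers usually have no follow-up calls after discharge outside certain programs. A study call may therefore be one of the few occasions on which someone hears that a caregiver is in crisis. The protocol does not tell the person on that call what to do.

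**Working it through.** No figure in the plan needs to be reproduced. The check sets the callers named in Section 6 against the role named in the Section 7 rule.

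| Planned call | Relative to randomization | Caller | Who is called | Distress action stated for that caller |
|---|---|---|---|---|
| Recruitment and screening | before | study staff | not yet allocated | none |
| Baseline, with CES-D | before | data collector | not yet allocated | none |
| Sessions 1-8 | after | interventionist | intervention arm | both tiers |
| Post-test 1, with CES-D | after | blinded data collector | both arms | none |
| Post-test 2, with CES-D | after | blinded data collector | both arms | none |
| Qualitative interview | after completing the intervention | data collector | 8-12 intervention caregivers | none |

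Planned calls after randomization, per caregiver:

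- Standard care: 2 post-tests, of which the interventionist makes 0. Result: 0 of 2.
- Intervention arm: 8 sessions + 2 post-tests = 10, of which the interventionist makes 8. Result: 8 of 10. For the 8-12 caregivers also interviewed: 8 + 2 + 1 = 11, so 8 of 11.

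Before randomization there are two calls (taking recruitment and screening as one). Neither is assigned to an interventionist. They belong to no arm, because allocation follows the baseline assessment.

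Time without a scheduled interventionist call in the intervention arm: post-test 1 comes 1-2 weeks after the intervention ends, and post-test 2 comes 12-13 weeks after post-test 1. The last session therefore precedes post-test 2 by 1 + 12 = 13 to 2 + 13 = 15 weeks.

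Number of post-test calls to standard-care caregivers, assuming the 227 are split evenly (113 or 114 per arm): at most 2 x 114 = 228. If the protocol's 10% drop out before post-test 1, the number is 2 x 0.9 x 113 = 203. The sample-size paragraph also mentions 145 per group, which would give 2 x 145 = 290, or 0.9 x 290 = 261 with the same dropout. These numbers describe workload. They say nothing about how often severe distress would be heard.

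Text that might fill the gap:

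1. Section 7 says "The interventionist(s) conducting the telephone interviews will receive extensive training", which could make the interventionist the assessment caller. But the Intervention paragraph lists interventionist and data collector as two separate hires, and the Data collection procedures give the assessments to the data collector.
2. The Randomization paragraph has the interventionist obtain the allocation from the project coordinator. It does not say who tells the caregiver, and it schedules no interventionist call to standard care.
3. The closing training sentences cover all personnel, but state neither a trigger nor an action for distress.
4. The abuse rule does give all study personnel an action. The authors therefore used the wider term when they wanted it, and the distress rule does not use it.

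**The case against.** The strongest reply is that this is loose wording and not an uncovered group. Section 7 may use the word interventionist for whoever is on the telephone. Its reference to telephone interviews and its any-arm language fit that reading, and the Specific Aims give the follow-up calls simply to a study team member. Caregiver distress is a named risk, and all personnel are to be trained against foreseeable risks. A step-by-step manual, described under Fidelity Considerations, covers recruitment and data collection and is a natural place for a caller's distress procedure. The study is described as minimal-risk.

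Much of this stands as mitigation. The manual may well contain the procedure, so the claim can only be that the protocol does not state it. The loose-wording reading does not survive the Data collection procedures, which give both post-tests to a blinded data collector. An interventionist delivering the sessions would know the arm and could not fill that role.

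Some stronger readings are tempting and are not supported:

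- A reader might count four uncovered standard-care calls. Two of them precede randomization, so the arm-specific gap is two calls.
- A reader might take the severe tier as expressly covering any arm. Only the lower tier says so. For the severe tier it is a natural inference.
- A reader might conclude that callers other than interventionists have no safety instruction at all. They do have one for suspected abuse or neglect.
- A reader might treat the number of CES-D interviews as a measure of risk. The documents give no rate of severe distress. The figure of over 45% in the session table concerns scores above a depressive-symptom cut-off in earlier research, and the instruments table says the CES-D is not a clinical measure.
- A reader might infer bias in the CES-D comparison. Nothing in the documents shows it.

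**Conclusion.** The concern holds in a limited form. As written, the distress rule is intended for every arm but depends on a role with 0 of 2 planned post-randomization calls in standard care, against 8 of 10 in the intervention arm (8 of 11 for those interviewed). The same gap affects the screening and baseline calls, the intervention arm's post-tests and the 8-12 qualitative interviews.

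This rests on three assumptions: that Section 6 describes the roles accurately, that any interventionist contact with standard care is incidental and unscheduled, and that the unseen manual does not count as protocol text. If the manual already holds such a rule, the remaining task is to bring the protocol into line with it. The point concerns safety and does not touch the estimand, the power or the primary analysis. It merits an amendment because a stated protection does not reach the people it names, and the correction is small.

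**What to change.** Amend Section 7 by widening the two existing tiers. A second, parallel rule would leave interventionists with two instructions for severe distress.

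1. In both tiers, replace the interventionist as the only assessor with wording such as: *any study personnel in contact with a caregiver in either arm, including recruitment callers and data collectors*.
2. Keep the existing content: serious changes in health, the study physician co-investigator, the VA social worker and primary care providers, 911, and the Caregiver Support Line.
3. Add: *A caller who is not an interventionist and hears possible severe distress, crisis or risk of harm will pass this at once to a study physician co-investigator, or call 911. The physician judges severity. The hand-off will not disclose the caregiver's arm to the data collector.*

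The word *possible* sets a low threshold on purpose. The Data collection procedures ask the data collector for Spanish fluency, communication ability and training in the assessments, not for clinical judgement.

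The cost is a short amendment with matching manual text, a brief addition to training already planned, and a study physician who can be reached while calls are being made. No participants or visits are added. Some referrals will prove unnecessary, and extra clinician contact in standard care could slightly narrow the CES-D difference. That is an acceptable price for a protection the protocol already intends.

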
## **8. Possible Benefits:**

There are no direct benefits from this study. Participants may benefit from learning problem-solving techniques if assigned to the study intervention. These problem-solving techniques may help them adjust to their roles as caregivers. Also, participants may benefit from using the information, tools, and resource lists on the RESCUE stroke caregiver website. Possible future benefits are identification of best practices for improving transitional care for informal caregivers of Veterans post-stroke.

## **9. Conflict of Interest:**

There is no conflict of interest relating to the Investigators and this protocol beyond the professional benefit from academic publication or presentation of results.

